1.2 Rationale for Conducting the Study

Cardiac surgery with CPB causes a massive consumptive coagulopathy and thrombotic complications in a similar way that disseminated intravascular coagulation does. Therefore, suppressing excessive hemostatic activation is a plausible therapeutic strategy that may impact postoperative morbidity.

Several studies have consistently reported the association of low postoperative AT levels with poor clinical outcomes (28, 38, 39) and that preoperative AT supplementation is able to maintain AT levels within a normal range throughout the postoperative period. (40, 41) Conversely, past studies have also highlighted the potential anticoagulant action of purified AT. (31, 34) Likewise, a dose dependent trend towards higher bleeding rates and a trend

towards an increased incidence of postoperative complications (namely bleeding related) in AT treated patients reaching the ICU with exceptionally high AT levels has been reported. (40, 41) The latter observations generate the hypothesis that an AT supplementation strategy aimed to avoid both excessively low (<58%) and excessively high (>100%) postoperative AT levels may represent an effective therapeutic goal to ameliorate the occurrence of bleeding and thrombotic events, respectively. However, these assumptions have been derived from post-hoc analysis and small studies performed with a limited number of patients. (40, 41)

Thus, this clinical study has been designed to evaluate the safety and efficacy of a preoperative treatment with AT supplementation (Antithrombin III [Human]) in subjects who undergo high-risk cardiac surgery with CPB targeting AT levels in such a way to avoid both excessively low and excessively high postoperative AT activity levels and to assess if management of AT levels in this range may decrease negative clinical outcomes during the ICU and hospital stay. The present clinical trial is intended to assess if directed preoperative AT supplementation will show favorable trends in decreasing the incidence of a composite of major morbidity when compared to placebo.

Antithrombin III (Human) with the trade name of THROMBATE III® is marketed in several countries for replacement therapy in subjects with hereditary deficiency of AT during pregnancy or surgery, or if at risk of thromboembolism. For simplicity, Antithrombin (Human) is abbreviated as AT-III (Human) in this protocol. Please refer to AT-III (Human) IB for additional detail.

2 STUDY OBJECTIVES

2.1 Primary Efficacy Objective

The primary objective of this clinical study is to compare the percentage of subjects with any component of a major morbidity composite between 2 groups of subjects randomly allocated to receive preoperative supplementation of AT-III (Human) or Placebo.

2.2 Secondary Efficacy Objectives

The secondary objectives of this clinical study are the following:

1. To compare postoperative AT levels at the ICU admission between the AT-III (Human) treatment group and Placebo control group
2. To compare the following postoperative outcomes between the AT-III (Human) treatment group and Placebo control group:
 - Postoperative chest-drain blood loss in the first 12 and 24 hours after surgery
 - Transfusion requirements
 - Need for surgical reexploration
 - Low cardiac output syndrome

- Myocardial infarction
- Stroke
- Acute kidney injury
- Arterial or venous thromboembolic events
- Infections
- Prolonged mechanical ventilation (>24 hours)
- All-cause postoperative mortality
- ICU stay duration
- Prolonged ICU stay (>6 days)
- Length of hospital stay

2.3 Safety Objectives

Safety objectives include evaluation of AT-III (Human) for clinical safety including adverse events (AEs), risks for bleeding, clinical laboratory testing, physical exam, and vital signs.

3 INVESTIGATIONAL PLAN

3.1 Study Design and Plan

[figure not shown]
This study will be a prospective, multicenter, randomized, double-blind, placebo-controlled study. Participating subjects will be 404 adult subjects undergoing cardiac surgery with CPB who will be randomized into two treatment groups preoperatively in a 1:1 ratio: AT-III (Human) treatment group and Placebo control group. All subjects will be stratified by their previous history of MI. Subjects undergoing complex/combined procedures will not be prescreened or screened for AT levels using local lab values to assess eligibility. Only subjects undergoing isolated CABG or single valve repair/replacements and not receiving preoperative heparin may be prescreened locally for AT levels (must be AT <80%).

Subjects randomized to AT-III (Human) treatment group will receive preoperative supplementation with AT-III (Human) designed to achieve an absolute increase (Δ) of 20% (percentage points) above pretreatment AT levels. Subjects randomized to Placebo control group will receive 0.9% Sodium Chloride (NaCl) for Injection, USP (United States Pharmacopeia).

The maximum study duration for a given subject will be approximately 7 weeks (48 days). There will be 2 weeks for prescreening and screening, and randomization into one of the two study groups (AT-III [Human] treatment or Placebo control). After the 2-week prescreening and screening period, the cardiac surgery procedure will take place with the preoperative administration of AT-III (Human) or Placebo supplementation. After surgery, the subject will be admitted to the ICU and be followed for approximately 1 month (30±4 days).

Both the primary efficacy endpoint (percentage of subjects with any component of the major morbidity composite) and the secondary endpoints will be evaluated for each subject after each cardiac surgery procedure, at the ICU admission, ICU discharge, and during a follow-up period of approximately 1 month (30±4 days) (see [Section 3.5.1](#)).

The overall study schema is shown in [Figure 3-1](#).

^a Randomization on Preoperative Visit (Day 0) may occur 24 hours before the day of surgery (Day 0).

^b If this visit coincides in time with the ICU discharge, the only assessments to be performed are those detailed in the ICU discharge visit. Regardless of when the ICU discharge takes place, AT activity levels should be measured on Postoperative days 1, 2, 3, and 5.

^c If the ICU stay is longer than 30 days, the assessments for both ICU Discharge visit and Follow-up visit (Day 30±4 days) will be performed at Day 30±4 days. There will be no additional ICU discharge visit and follow-up visit.

Figure 3-1 Overall Study Schema

3.2 Selection of Study Population

Subjects undergoing high-risk, non-emergency cardiac surgery with CPB will be studied. Subjects undergoing isolated CABG or single valve repair/replacements maybe prescreened for AT activity measured locally which should be below 80% unless treated with preoperative heparin (details below). Four hundred and four (404) subjects will be enrolled in this study.

3.2.1 Inclusion Criteria

A subject must meet all the following inclusion criteria to be eligible for participation in this study:

1. Male or female.
2. At least 18 years of age.
3. Subject needs non-emergency cardiac surgery with cardiopulmonary bypass.
4. Types of cardiac operations permitted:
 - Complex/combined procedures (CABG+valve), double/triple valve repair/replacements, ascending aorta/aortic arch surgeries (without baseline AT level restriction or preoperative heparin requirement). OR
 - Isolated CABG or single valve repair/replacements are allowed only if either (a) AT level is less than 80% OR (b) preoperative heparin is received (unfractionated heparin [UFH] for at least 12 hours; low-molecular-weight heparin [LMWH] for more than 5 days).
5. Not applicable – intentionally left blank for data management purposes (consistency in eCRF capture of eligibility criteria historically).
6. Subject has signed informed consent form.
7. Subject is willing to comply with all aspects of the protocol, including blood sampling, for the total duration of the study.

3.2.2 Exclusion Criteria

A subject meeting any of the following exclusion criteria is NOT eligible for participation in the study. All exclusion criteria involving hematology/coagulation and clinical chemistry determinations will be based on local lab results.

1. Subject needs emergency surgery.
2. Subject needs heart transplantation.
3. Use of minimally invasive surgery.
4. Previous cardiac operation.
5. Infective endocarditis.

6. Thromboembolic events, stroke, or ST-elevated myocardial infarction within 7 days of surgery.
7. Cardiogenic shock at the time of surgery.
8. Renal dysfunction: Creatinine levels >2 mg/dL or chronic dialysis.
9. Liver dysfunction: AST, ALT increase ≥ 2 -fold above the upper-limit of local lab normal ranges.
10. Treatment with Clopidogrel and Ticagrelor within 5 days before surgery, Prasugrel within 7 days before surgery, glycoprotein IIb/IIIa receptor blockers within 24 hours of surgery.
11. Treatment with new oral anticoagulants (Apixaban, Rivaroxaban, Dabigatran) within 48 hours before surgery.
12. Vitamin K antagonist therapy and an international normalized ratio >1.3 on the day of surgery.
13. Platelet count $<120,000/\mu\text{L}$.
14. History or suspicion of a congenital or acquired coagulation disorder.
15. History of anaphylactic reaction(s) to blood or blood components.
16. Allergies to excipients in the study drug.
17. Refusal to receive allogenic transfusion of blood-derived products.
18. Received AT treatment within the last 3 months prior to Screening visit.
19. Subject is pregnant.
20. Subject has participated in any another investigational study within the last 3 months prior to Screening visit.

3.3 Treatments

3.3.1 Treatments to Be Administered

3.3.1.1 AT-III (Human)

Detailed information of AT-III (Human) is also available in the IB.

AT-III (Human), a freeze-dried preparation for intravenous (IV) administration, has AT as the active ingredient. It is obtained from human plasma by a continuous purification process, which is performed in an authority-regulated plant in Clayton, North Carolina. Antithrombin is the main inhibitor of blood coagulation.

AT-III (Human) is prepared from pooled units of human plasma from normal donors by modifications and refinements of the cold ethanol method of Cohn. When reconstituted with sterile water for injection (SWFI), USP, AT-III (Human) has a pH of 6.0–7.5, a sodium content of 110–210 mEq/L, a chloride content of 110–210 mEq/L, an alanine content of

0.075–0.125 M, and a heparin content of not more than 0.1 IU heparin/IU ATIII. AT-III (Human) contains no preservative and must be administered by the IV route.

AT-III (Human) preparation will be reconstituted in 10 mL SWFI, which will be transferred into the vial containing the concentrate.

Usually the solution is clear or slightly opalescent. Do not use solutions that are cloudy or have deposits. Infusion of AT-III (Human) should be started within 3 hours of study drug reconstitution. It should be kept at room temperature not to exceed and precautions must be taken to avoid microbiological contamination. It should not be stored in the refrigerator or mixed with other drugs. Leftover product must never be kept for later use.

3.3.1.2 Placebo

Placebo used in this study will be 0.9% Sodium Chloride (NaCl) for Injection, USP.

3.3.1.3 Labeling of Investigational Products

Investigational products will be labeled according to the requirements of local law and legislation. Label text will be approved according to agreed Grifols procedures, and a copy of the labels will be made available to the study site.

Each vial of AT-III (Human) will be labeled with the antithrombin potency expressed in international units (IU) as defined by the World Health Organization (WHO).

3.3.1.4 Storage of Investigational Products

The investigational product should be stored at temperatures not to exceed 25°C (77°F). Do not freeze. The investigational product must be stored in a secure area accessible only to the unblinded pharmacist, or designee, until dispensed for the study subject.

3.3.1.5 Accountability for Investigational Products

Investigational product is to be used only for the study in accordance with the directions given in this protocol. The Investigator, or designee such as the study pharmacist, is responsible for the distribution of the investigational product in accordance with directions given in the protocol and pharmacy manual.

The Investigator is responsible for maintaining accurate records of the investigational product for his/her site. Investigational product inventory/dispensing documentation verifying the receipt, dispensing, destruction, or return must be maintained and kept current by the unblinded pharmacist. The inventory must be made available for inspection by the monitor. Investigational product supplies (including placebo) must be accounted for by the monitor and inventory/dispensing logs must be verified by the monitor prior to Investigational product return or destruction. Written documentation of any used and unused

inventory is required. At the end of the study, a copy of the inventory/dispensing log(s) will be retrieved by the monitor and returned to Grifols Therapeutics Inc.

Any unused investigational product will be accounted for and returned to the Sponsor's distributor. When required by local policies, unused supplies may be destroyed at the study site. The Investigator will ensure that such disposition does not expose subjects to risks from the investigational product. The Investigator and the Sponsor's representative will maintain records of any such alternate disposition to permit accurate drug accountability.

3.3.2 Rationale for Selection of Doses/Timing of Investigational Products in the Study

3.3.2.1 Study Drug Doses

Every subject allocated in the AT-III (Human) treatment group will receive, immediately after anesthesia induction, a single dose of AT-III (Human) sufficient to achieve an absolute increase (Δ) of 20% (percentage points) above pretreatment AT levels according to the formula:

$$AT - III \text{ dose (IU) required} = \frac{(20) \times (\text{subject weight in kg})}{1.4}$$

The only variable in the equation is the subject's body weight. For calculating AT-III (Human) dose, subject's weight obtained during the Screening visit will be used.

AT-III (Human) or Placebo (0.9% NaCl) will be prepared according to the volume calculated by unblinded pharmacist or designee and will be infused intravenously.

AT-III (Human) will not be administered postoperatively unless the Investigator decides otherwise for clinical reasons (if this is the case, the subject will be excluded from the efficacy analysis).

After the operation, all subjects will be admitted to the ICU and will be followed for approximately 1 month regardless of when the ICU discharge takes place (see [Section 3.6.2](#)).

3.3.2.2 Rationale for Selection of Doses in the Study

The goal for dose selection is to avoid both low and high postoperative AT levels in treated subjects. In a previous study using another AT product for the same indication ([40](#)), the preoperative AT target of 120% was explored. The results suggested that dosing of subjects with a preoperative AT target of 120% resulted in a large number of AT treated subjects reaching the ICU with high postoperative AT levels ($>100\%$). These AT levels were associated with an overall worse postoperative outcome. To build on this study, a more conservative dosing scheme and the inclusion of more severe subjects (i.e., undergoing complex/combined cardiac surgeries or subjects undergoing isolated procedures with low

preoperative AT levels or treated with heparin preoperatively) are intended to achieve better efficacy and safety.

3.3.3 Method of Assigning Subjects to Treatment Groups

3.3.3.1 Subject Numbering

Within each study site, subjects in the study will receive a consecutive subject number. Subject numbers are generated beginning with the study center number (3 digits, assigned by the sponsor) followed consecutively with a unique number for each subject (4 digits, including leading zeros). For example, if the Investigator's center number is 301, subject number will be 3010001, 3010002, 3010003, etc., in consecutive order. Subject numbers, once assigned, will not be reused at any center.

3.3.3.2 Randomization

Subjects will be randomized into one of two treatment groups: AT-III (Human) treatment group and Placebo control group. Subjects will be stratified by their previous history of myocardial infarction (MI). Unblinded pharmacist or designee will obtain the treatment assignment based on a computer-generated randomization schedule. The randomization number will be assigned at Preoperative visit (Day 0) after all enrollment criteria are met.

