same standard of care without the administration of AT. Preoperative supplementation of AT yielded significantly higher AT activity levels compared to untreated patients not only at the ICU admission, but throughout the entire postoperative stay until ICU discharge. Moreover, 25 patients in the control group (26%) presented postoperative AT activity levels below 58% whereas no patients in the treatment group (0%) reached the ICU with AT levels below this threshold. In addition, patients in the AT arm had a significantly lower rate of heparin resistance and a trend towards fewer thromboembolic events. However, a higher postoperative bleeding rate (8 mL/hour) was observed in the treatment group, but was judged by the investigators not to be clinically significant. Conversely, due to the lack of statistical power, differences in postoperative outcomes were unattainable between study groups.

Post-hoc analysis of the abovementioned study confirmed previous observations that low postoperative AT levels (<58%) are a consistent predictor of prolonged ICU stay (>7 days) in untreated patients. Further, patients presenting ICU-AT levels below this threshold suffered overall worse postoperative outcome than patients that reached the ICU with AT levels above 58% regardless of their treatment suggesting that prophylactic measures to avoid such low AT levels after CPB are warranted. On the other hand, a similar pattern was observed in patients reaching the ICU with unexpectedly high AT activity levels. The latter were more prone to suffer bleeding-related postoperative complications suggesting that AT overcorrection should also be avoided and that a preoperative AT target of 120% may be excessive. Moreover, given that this study was performed with less complex procedures such as isolated CABG or single valve, compared to more complex/combined procedures such as double/triple valve repair/replacement, ascending aorta/aortic arch surgeries, with normal baseline AT values, many subjects in the control group reached the ICU with AT levels within the normal physiological range, suggesting that an AT supplementation may be of more benefit in a higher risk patient population (undergoing complex/combined cardiac surgeries with long bypass runs and/or high inflammatory response) prone to consume large amounts of AT or with lower baseline AT levels.

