5.1.3 Efficacy Analysis

5.1.3.1 Primary Efficacy Analyses

The primary efficacy variable is the percentage of subjects with any component of the composite of major morbidity. The primary efficacy variable will be analyzed with Cochran Mantel Haenszel test adjusting for history of MI using ITT population. The sensitivity analyses using PP populations will also be provided.

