10.1 Primary Efficacy Analyses

Number and Percentage of subjects with any component of a major morbidity composite will be summarized by treatment and analyzed using Cochran Mantel Haenszel test adjusting for history of MI based on mITT population. Sensitivity analyses using PP population or mITT population minus subjects with postoperative AT administration per investigator's discretion will also be provided.

Subgroup analyses by age group, gender, and surgery type (isolated CABG vs. all other surgeries per medical review of all surgical procedures) will be performed for both mITT and PP populations, as well as mITT population minus subjects with postoperative AT administration.

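### The primary test adjusts for MI history only; adding the entry route of inclusion criterion 4 would cheaply protect the result against chance imbalance

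*Protocol*

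**What the plan says.** **Two ways in.** Protocol 3.2.1, criterion 4, lists one group as "Complex/combined procedures (CABG+valve), double/triple valve repair/replacements, ascending aorta/aortic arch surgeries", with no AT limit and no heparin condition. For the other group, "Isolated CABG or single valve repair/replacements are allowed only if either (a) AT level is less than 80% OR (b) preoperative heparin is received".

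**One stratification factor.** Protocol 3.3.3.2: "Subjects will be stratified by their previous history of myocardial infarction (MI"). SAP 5.4 says the same.

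**One adjustment factor.** Protocol 5.1.3.1: "The primary efficacy variable will be analyzed with Cochran Mantel Haenszel test adjusting for history of MI using ITT population". SAP 10.1 changes the population but not the adjustment: "analyzed using Cochran Mantel Haenszel test adjusting for history of MI based on mITT population".

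**Surgery type appears only as a subgroup.** SAP 10.1 plans subgroup analyses of the primary endpoint by "surgery type (isolated CABG vs. all other surgeries per medical review of all surgical procedures"). That cut places single-valve subjects with the double-valve and aortic cases, so it is not the cut made by criterion 4.

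**What is said about risk.** Protocol 1.1 describes a higher-risk population "undergoing complex/combined cardiac surgeries with long bypass runs and/or high inflammatory response", or with lower baseline AT. The Amendment 3 rationale expects longer bypass and more AT consumption in complex/combined surgery. Protocol 3.3.2.2 groups both admitted routes together as the more severe subjects. Protocol 5.2 and SAP 5.3 use one overall placebo rate, 22.0%, and give none by route.

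**The concern.** Entry route is a baseline fact that eligibility review has to establish before randomisation. The protocol links complex surgery to longer bypass and greater AT consumption. The composite counts ventilation beyond 24 hours, reexploration, acute kidney injury and death. Route is therefore plausibly prognostic, although the documents do not show by how much.

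MI history is a poor stand-in for it. A double-valve or aortic-arch subject may have no prior infarction, while an isolated-CABG subject may well have one.

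If route is prognostic, leaving it out has two effects. Some removable variation stays in the error. And in the single trial that is run, an excess of complex cases in one arm passes into the estimated treatment difference. The trial looks for a trend at alpha 0.15 with 70% power and a 7.7-point target, so a shift of a point or two could alter whether a trend is declared. A subgroup table does not correct the primary estimate.

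**Working it through.** **1. The plan's own figure.** Inputs from Protocol 5.2: p1 = 0.22, p2 = 0.143, alpha 0.15 (sidedness not stated), power 70%, 192 per arm. Write q = 1 - p, with mean p = 0.1815.

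n = [1.4395 × √(2 × 0.1815 × 0.8185) + 0.5244 × √(0.22 × 0.78 + 0.143 × 0.857)]² / 0.077² = [0.7847 + 0.2844]² / 0.005929 = 192.8, so 193 per arm. With unpooled variance it is 191.4, so 192. The stated 192 therefore reproduces as a two-sided test without continuity correction (one-sided would give 122).

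Power at 192: Φ[(0.077 × √192 - 0.7847) / 0.5424] = Φ(0.520) = 69.9%.

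**2. Assumptions, none of them in the documents.** 60% complex; placebo rates (complex/isolated) of 26/16, 28/13 or 30/10, each averaging 22% (for example 0.6 × 26 + 0.4 × 16 = 22.0); relative risk 0.65 in both routes. MI strata are left out because their rates are not given.

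**3. Average power with route as a stratum.** Replace both variances by their within-route averages. For 26/16:
- null: 2 × [0.6 × 0.2145 × 0.7855 + 0.4 × 0.132 × 0.868] = 0.2938
- alternative: 0.6 × (0.1924 + 0.1404) + 0.4 × (0.1344 + 0.0932) = 0.2907
- power: Φ[(1.0669 - 1.4395 × √0.2938) / √0.2907] = 70.2-70.3%

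The other splits give 70.7% and 71.4%, so the gain over 69.9% is about 0.4 to 1.5 points. Simulation of the actual tests moves power from about 70.3% to 70.5-71.6%.

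A wider simulation (200,000 trials per setting, complex share 30-70%) gives:

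| Placebo risk ratio, complex:isolated | Power, unstratified | Power, route-stratified |
|---|---|---|
| 1 | 70.3% | 70.0-70.1% |
| 1.5 | 70.2-70.3% | 70.2-70.4% |
| 2 | 70.1-70.4% | 70.7-70.8% |
| 3 | 70.2-70.4% | 71.2-72.6% |

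Type I error was 0.149-0.152 for both tests throughout.

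**4. How often the arms differ.** SD of the difference in complex share = √(2 × 0.6 × 0.4 / 192) = 0.050. A gap of 5 points or more (1 SD) occurs in about 32% of trials, and one of 10 points or more (2 SD) in about 4-5%. Over complex shares of 30-70% the ranges are 28-33% and 3-5%.

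**5. What a gap does.** On placebo rates, a 10-point gap shifts the risk difference by 0.10 × (10, 15 or 20 points) = 1.0, 1.5 or 2.0 points, which is 13-26% of 7.7. Under the planned effect the shift is multiplied by (1 + 0.65)/2 = 0.825.

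Power of the test without route, given the gap:

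| Gap in complex share | 26/16 | 28/13 | 30/10 |
|---|---|---|---|
| AT-III 5 points higher | 66% | 64% | 63% |
| AT-III 5 points lower | 74% | 75% | 77% |
| AT-III 10 points higher | 62% | 58% | 54% |
| AT-III 10 points lower | 77% | 80% | 83% |

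With no true effect and AT-III 10 points lower, the chance of a favourable trend rises from 7.5% to 11%, 14% or 16%. In simulated trials where AT-III has at least 5 points more complex cases, adding route restores power from about 58-64% to about 70-71%.

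**The case against.** **Nothing is invalid.** The test adjusts for the factor used in randomisation. Chance imbalance in other covariates is already part of its sampling error and favours either arm equally often. This stands in full. Other unstratified factors may be prognostic too; what sets route apart is that it defines eligibility.

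**The effect is small and rests on assumed rates.** This also stands. The standard error of the risk difference is √[(0.1716 + 0.1226)/192] = 3.9 points, so a 10-point gap moves the estimate by 1.0/3.9 to 2.0/3.9, or 0.26 to 0.51 standard errors, in about one trial in twenty. The average power gain alone would not justify changing a primary analysis.

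**The protocol does not rank the two admitted groups by risk.** A reader might infer that it does, because the Amendment 3 rationale speaks of low-risk patients having isolated procedures. That phrase describes earlier studies. Low AT or heparin is required precisely to bring isolated cases into the high-risk population, and Protocol 3.3.2.2 names both groups as more severe. A difference in event rate is plausible but inferred.

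**The SAP already looks at surgery type.** It does, in subgroups, and it summarises procedure type, bypass time and clamp time. These could reveal an imbalance but would not adjust for it, and the subgroup cut differs from criterion 4.

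**It is late, and the data may not fit.** The SAP was written with the study under way: an eCRF page had been added, and more subjects than expected had gone undosed. Changing the randomisation schedule is therefore probably moot and is not proposed. Subjects enrolled under the earlier criteria can still be classified by procedure type. One practical point stands: the visit lists record the procedure at the operative visit and show no separate planned-procedure field.

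**Conclusion.** The point holds as a question of precision and of protection against chance imbalance. It is not one of bias or error control. The plan leaves a defining, plausibly prognostic baseline factor out of the primary test.

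Under the assumed rates the average gain is about 0.2 to 1.5 power points. The larger benefit comes in the roughly one trial in three where complex share differs by 5 points or more, and above all in the 4-5% with 10 points or more, where the risk difference moves by about 1 to 2 points. If route is not prognostic these benefits vanish and about 0.2-0.3 points of power are lost.

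The documents do not support a claim that the sponsor regards the two routes as unequal in risk, that the planned test is biased, or that the sample size must change. The case for acting is that adjustment is cheap and the factor has to be known for eligibility.

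**What to change.** Before unblinding, amend SAP 10.1:

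- **Primary CMH strata:** MI history by entry route, with route defined as complex/combined versus isolated CABG or single valve, using the procedure planned at eligibility. Keep the MI-only CMH as a sensitivity analysis and record the change in SAP 13.
- **At minimum:** leave the primary test as it is and prespecify the route-adjusted CMH as a sensitivity analysis.
- **Subgroup:** align the surgery-type split with criterion 4, so that single-valve subjects are grouped with isolated CABG.

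Cost: a short SAP edit and four strata instead of two, with about 0.2-0.3 points of power lost if route carries no prognostic information. Planned route must be derived blind from eligibility records, and its availability should be confirmed first. The sample size and the randomisation schedule stay as they are.
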